10.1.1. Additional Observational Visit

We have noted in the open label portion of the SEL-212/101 clinical trial and the initial portion of this SEL-212/201 clinical trial a persistent and beneficial effect on serum uric acid (sUA) when subjects are given SEL-212. This effect had persisted beyond 30 days in 17 of 31 subjects as of November 28, 2016. Based on these results, our goal is to follow subjects in Cohorts 3-8, 10, 11, and 12 beyond the current protocol Treatment Period 5, Day 30 Visit so that we may monitor and characterize the continued effect of SEL-212. Since there is a lag between lab results and the visits we would propose to see the subject for an additional visit if the sUA at the Treatment Period 5 Day 21 (Visit 32) is below 6 mg/dL. The additional visit would be 60 ± 1 days after the Treatment Period 5 Day 0 dosing day (Visit 28) at which time we would have the value of the sUA for the Day 21 (Visit 32) visit and their end of study visit (EOS P5 Day 30) value. The beneficial effect on the sUA is an unexpected, positive event which is beneficial to the subject and would likely be beneficial to the projected treatment population in the future.

In Part C (Cohorts 13, 15, and 17), subjects will be followed as described above.

Blood samples will be taken at the observational visits for assessments that will include: serum uric acid, and serum samples for anti-pegsiticase, anti-uricase and anti-PEG.

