6.2. KEY DEFINITIONS

The last non-missing value prior to the start of infusion of any study drug in Period 1 will be used as baseline.

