9.3. PHARMACODYNAMICS PARAMETERS

The following PD parameters will be calculated based on actual measurements of PD uric acid for each Cohort and Treatment period and Overall where possible:

C_{min}	Minimal observed serum concentration
T_{min}	Time of minimal observed serum concentration
CFB_{min}	Minimum observed change from baseline in serum concentration
$AUE_{CFBlast}$	Absolute value for Area under the change from baseline in effect-time curve from time zero to the time of the last quantifiable concentration (effect - uric concentration)
$TA_{AUE_{CFBlast}}$	Time adjusted area under the absolute value for effect-time curve from time zero to the time of last quantifiable concentration (effect - uric concentration)
T_{onset}	Time of onset of effect - first time point of reduction uric acid concentration >10% of baseline
$T_{resolve}$	Time of resolution of effect - first time point of return of uric acid concentration to baseline defined as <10% difference from pre-dose baseline
$T_{duration}$	Time of duration of effect, calculated as $T_{resolve} - T_{onset}$

The following PD parameters will be calculated based on %CFB of PD uric acid for each Cohort and Treatment period and Overall where possible

Statistical Analysis Plan

$\%CFB_{\min}$	Minimum %CFB in serum concentration
$AUE_{\%CFB_{\text{last}}}$	Absolute value for Area under the %CFB in effect-time curve from time zero to the time of the last quantifiable concentration (effect - uric concentration)
$TA_AUE_{\%CFB_{\text{last}}}$	Time adjusted area under the %CFB for effect-time curve from time zero to the time of last quantifiable concentration (effect - uric concentration)
# and % of patients with $SUA < 6$ in TP3	The number and % of patients maintaining sUA concentrations below 6 mg/dL at the end of treatment period 3
# and % of patients with $SUA < 6$ in TP5	The number and % of patients maintaining sUA concentrations below 6 mg/dL at the end of treatment period 5

9.3.1. Handling of Dropouts, Missing Data or Data Below the Lower Limit of Quantification

Missing concentration data for all subjects who are administered scheduled study treatments will be considered as non-informative missing and will not be imputed. No concentration estimates will be provided for missing sample values.

For the derivation of PD parameters, serum concentration summary, individual serum concentration versus time curves and mean concentration versus time graphs the following rules will apply:

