- Concentration values below the assay's lower limit of quantification (BLQ) for all time points will be treated as zero
- The sampling time of pre-dose samples relative to dosing will also be treated as zero
- If the actual time of sampling is missing, the planned time may be used
- In case of discrepancy between the nominal time and time stamp on the sample concentration data, which affects the temporal order of PD samples and is not related to documented protocol deviations, the nominal (planned) time will be used only for the pre-dose samples before treatment period 1. All other data with such time discrepancy will be removed from PD parameter derivations and summaries. The profiles for subjects with the single PD points removed due to this type of discrepancy can still be used for derivation of PD parameters and any summaries or models for other PD time points.

Statistical Analysis Plan

Samples taken outside the sampling windows may be excluded from by-time point summary statistics. This will be determined prior to the start of analyses around database lock.

No further imputation will be applied to any missing values.

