9.4. DATA SUMMARIZATION

PD parameters and serum concentration data will be summarized by Treatment period and Cohort using the following descriptive statistics:

PD Summary Statistics:

Variable	Summarized with:
Serum concentration at each nominal time point	n, number and % BLQ, arithmetic mean, SD, CV%, minimum, median and maximum
CFB _{min} , %CFB _{min} , AUE _{CFBlast} , AUE _{%CFBlast} and TA_AUE _{CFBlast} , TA_AUE _{%CFBlast}	n, arithmetic mean, SD, CV%, minimum, median, maximum, geometric mean and geometric CV%
T _{onset} , T _{resolve} , T _{duration} , and T _{min} (actual time)	n, minimum, Q1, median, Q3 and maximum

Mean concentrations will not be presented if 50% or more of the available observations relative to total number of subjects within the treatment at any time point are missing. BLQ values for uric acid concentration will be summarized as 0 (zero) for all time points.

Samples taken outside the allowed time windows may be excluded from summarization. This will be determined prior to database lock.

The following conventions will be used for the presentation of the descriptive statistics of PD parameters and serum concentrations for uric acid:

Statistical Analysis Plan

PD Reporting Precision:

Statistics	Degree of Precision
Minimum, Maximum	3 significant digits or as needed based on actual measured values (for example PD concentrations)
Mean (arithmetic and geometric), Median	4 significant digits or as needed based on actual measured values (for example PD concentrations)
Standard deviation	5 significant digits or as needed based on actual measured values (for example PD concentrations)
CV, Geometric CV	1 decimal point or as needed based on actual measured values (for example PD concentrations)

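### T_duration is defined only for subjects whose uric acid is seen to return to within 10% of baseline, so its summary describes relapsers and barely separates cohorts

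*SAP*

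**What the plan says.** SAP 4.2 and 9.3 derive three time parameters for uric acid, by cohort and treatment period and overall, where possible:

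- T_onset is the "first time point of reduction uric acid concentration >10% of baseline".
- T_resolve is the "first time point of return of uric acid concentration to baseline defined as <10% difference from pre-dose baseline".
- T_duration is "Time of duration of effect, calculated as" T_resolve minus T_onset.

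SAP 6.2 fixes the reference value: "The last non-missing value prior to the start of infusion of any study drug in Period 1 will be used as baseline". SAP 9.6 does the same for uric acid.

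On missing values, SAP 9.3.1 states: "Missing concentration data for all subjects who are administered scheduled study treatments will be considered as non-informative missing and will not be imputed". It closes with "No further imputation will be applied to any missing values". SAP 9.4 summarises the three parameters by "n, minimum, Q1, median, Q3 and maximum". Neither document gives a censoring rule, an assigned maximum or a time-to-event method for a subject who does not return to baseline.

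Protocol 6.3.1 redoses subjects in Cohorts 3-8, 10-13, 15 and 17 only if Day 21 sUA is at or below 1.0 mg/dL. The others are followed to about Day 30 after the last dose and then leave. Protocol 10.1.1 says of the effect of SEL-212: "This effect had persisted beyond 30 days in 17 of 31 subjects as of November 28, 2016".

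**The concern.** How long uric acid stays low, with and without SEL-110, is a natural reading of the secondary pharmacodynamic objective. Under these definitions success produces a blank. A subject still suppressed at the last sample of a period has no T_resolve and no T_duration, and drops out of the quartiles. A stopped subject whose sUA has passed 1.0 mg/dL but is still more than 10% below baseline at the final visit also has none. The values that remain come from subjects who relapsed fully while under observation. The better SEL-110 works, the fewer subjects contribute, and the printed median says nothing about those who were protected.

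T_onset has a related fault. The reference is the Period 1 baseline, and continuing subjects usually reach the next dose still suppressed. In Periods 2-5 they meet the onset criterion before any drug is given.

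**Working it through.** The plan states no figure for duration, so there is none to reproduce. The check applies the definitions literally.

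**Who can have a value within a period.** Entry requires screening sUA of at least 6 mg/dL (Protocol 7.1). Assume the Period 1 baseline is also at least 6. The return threshold is then at least 0.9 × 6 = 5.4 mg/dL. A continuing subject in a SEL-110 cohort, at or below 1.0 mg/dL on Day 21, must rise by more than 5.4 − 1.0 = 4.4 mg/dL by the Day 28 pre-dose sample to resolve in that period. That will almost never happen. In Cohorts 1 and 2 the Day 21 limits for redosing are higher (below 6 mg/dL and not above 50% of baseline), so the exclusion need not fall equally across cohorts.

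**Rough size.**
- SEL-212: 17/31 = 54.8% with effect beyond 30 days, leaving 14/31 = 45.2% (Protocol 10.1.1).
- SEL-037 alone, single dose: 1/22 = 4.5% with effect to Day 30 (Protocol 4.3.2.1).

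Both are proxies, since neither count uses the 10% rule. Two assumed subjects show the difference from a 6 mg/dL cut. Baseline 6.3 and sUA 5.8 gives 5.8/6.3 = 92%, resolved although below 6. Baseline 9 and sUA 7 gives 7/9 = 78%, unresolved although above 6.

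**Constructed cohorts of 12 (assumed data, onset taken as Day 0).**
- A: 9 sustained to Day 28, 3 return on Day 14. Plan's summary: n = 3, median 14 days. Kaplan-Meier with censoring at Day 28: S(14) = 1 − 3/12 = 0.75, median not reached.
- B: 3 return on Day 14, 9 on Day 21. Plan's summary: n = 12, median 21 days. Kaplan-Meier: S(14) = 0.75, S(21) = 0.75 × (1 − 9/9) = 0, median 21 days.
- A cohort with all 12 sustained has n = 0 and no duration at all.

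A is the better cohort, yet the plan's median is shorter. Censoring restores the order.

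**How often this happens.** Simulation with 12 per cohort, 20,000 repeats, sustained shares 17/31 and 1/22, relapse on Day 7, 14, 21 or 28. Relapse-day probabilities are assumed: reference 0.25/0.35/0.25/0.15, early 0.40/0.35/0.15/0.10, late 0.15/0.30/0.35/0.20. The plan's median in the better cohort, relative to the other, is:

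| Relapse timing (better cohort; other cohort) | Shorter | Tied | Longer |
|---|---|---|---|
| Same (reference; reference) | 30% | 37% | 33% |
| Earlier in better cohort (early; late) | 75% | 19% | 6% |
| Later in better cohort (late; early) | 5% | 22% | 74% |

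With the same timing, changing the better cohort's sustained share to 30%, 55% or 80% leaves the chance of a shorter median at 29%, 30% and 31% (8,000 repeats each). The summary responds to when relapsers relapse and hardly at all to how many subjects relapse.

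**Onset.** SAP 9.3.1 sets the pre-dose sampling time to zero. A continuing subject still suppressed against the Period 1 baseline therefore meets T_onset at time zero in Periods 2-5. Reading the reference as each period's own pre-dose value does not help: values below quantification count as zero (SAP 9.3.1), and a percentage of zero gives no usable threshold.

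**The case against.** The strongest reply is that little hangs on T_duration. SAP 9.7 models other parameters: %CFB_min, the two areas under the effect curve, and Day 21 sUA and its percentage change. The box plots in SAP 9.6 and the correlations in SAP 9.7 also leave T_duration out. Sustained response is visible in those parameters, in the counts with sUA below 6 mg/dL at the end of Treatment Periods 3 and 5 (SAP 9.3, 9.6), and in the split at 1.0 mg/dL on Day 21 (SAP 10.4). The n is printed, with the cohort size in the column header (SAP 15.2.4), so n = 3 under N = 12 would be noticed. The overall derivation can give a late relapser a long value. This all stands and limits the harm. It does not supply a rule for unresolved subjects, and the 50% suppression rule in SAP 9.4 covers mean concentrations only, so a median from two or three subjects would still be printed.

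A second reply is that the reversed example depends on chosen relapse times. That also stands: with later relapse in the better cohort the order is wrong in only 5% of repeats.

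A third is that Kaplan-Meier estimation has its own bias here. Subjects stopped for Day 21 sUA above 1.0 mg/dL are losing response and are followed only to about Day 30, so censoring them is informative. That is correct, and the fix has to deal with it.

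**Conclusion.** The defect holds. Followed exactly, the plan omits sustained responders from a named pharmacodynamic endpoint, and the omission depends on outcome. The likely result is a table that cannot separate cohorts; a wrong order is possible, depending on relapse timing. T_onset in Periods 2-5 carries no information for continuing subjects.

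Two stronger readings are tempting. A reader might infer that the best cohorts will show the shortest durations. The documents give no relapse times for the relapsers in each cohort, so this remains a possibility. A reader might also infer that about 55% of SEL-212 subjects will have no value. The 17 of 31 pools the earlier SEL-212/101 study with early data from this one, and Protocol 10.1.1 does not define persistence by the 10% rule.

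The consequence is confined to a descriptive secondary parameter. The conclusion assumes that Period 1 baselines are mostly at or above 6 mg/dL and that suppression on Day 21 usually lasts to Day 28. It is worth correcting before database lock, and no primary conclusion depends on it.

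**What to change.** Amend SAP 9.3, 9.3.1 and 9.4 as follows.

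- Treat T_duration as right-censored at the last available sUA sample, including End of Study, Early Termination and Day 60 samples. For by-period values, censor at the next pre-dose sample. State that Early Termination samples feed this derivation, since SAP 6.1 otherwise only lists them.
- Report by cohort the number resolved, the number not resolved and the Kaplan-Meier median, given as not reached where applicable. If quartiles are kept, rank unresolved subjects as longer than their last sample time.
- Add first sUA at or above 6 mg/dL as a second event.
- Report subjects stopped under the Day 21 rule separately, and add a sensitivity analysis that counts that stop as loss of response.
- Derive T_onset for Period 1 only.

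The data are already collected. The cost is SAP wording and a little more programming, and some medians will not be reached.

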their premedication (date and medication, Day -7) for the prevention of gout flares. On the evening of Day -1 the subject will take their premedication of fexofenadine 180 mg orally. The day of initial dosing of study drug will be designated Day 0. On the morning of Day 0 subjects will report to the clinic for the dosing of study drug. 2 hours prior to the dosing of study drug SEL-110, the subject will receive fexofenadine 180 mg orally and 1 hour prior to the dosing of study drug SEL-110, subjects will receive methylprednisolone 40 mg (or equivalent drug) intravenously. Eligible subjects who have been assigned to Cohorts 3-8, 10, 11, and 12 will receive a single IV infusion of SEL-110 (dose based on a mg/kg basis) administered with a syringe infusion pump. In cohorts receiving SEL-110 doses <0.10 mg/kg, SEL-110 will be infused at a single steady rate sufficient to deliver the dose volume over a period of 55 minutes concurrently with a 60 minute infusion of 125 mL of normal saline. In cohorts receiving SEL-110 ≥ 0.10 mg/kg, the rate of SEL-110 infusion will be 5.5 mL/hour for the first 30 minutes and, then, will be changed to a steady rate sufficient to deliver the remainder of the dose volume for the additional 25 minutes, concurrently with a 60 minute infusion of 125 mL of normal saline. This will be followed (± 3 minutes) by an infusion delivered by infusion pump of SEL-037 (0.2 mg/kg for Cohorts 3, 5, 7, and 11; 0.4 mg/kg for Cohorts 4, 6, 8, 10, and 12) diluted into 100 mL of normal saline delivered over 60 minutes (± 2 minutes). If necessary the infusion time may be extended in order to ensure the infusion of the study medication in entirety. Subjects will remain in the clinic for 9 hours after the start of the infusion of SEL-110 for safety evaluations and PK blood draws (see Schedule of Events below). Subjects will return for PK and PD blood draws on Treatment Period 1, Days 1, 7, 14, 21 and safety and Antibody blood draws on Treatment Period 1, Days 7, 14, 21.

Part A – Treatment period 2

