T _{onset}	Time of onset of effect - time of reduction uric acid concentration >10% of baseline
T _{resolve}	Time of resolution of effect - time of return of uric acid concentration to baseline defined as <10% difference from pre-dose baseline
T _{duration}	Time of duration of effect, calculated as T _{resolution} - T _{onset}

Statistical Analysis Plan

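### T_resolve is defined as an undirected difference of less than 10% from baseline, so, read literally, uric acid that rebounds above 110% of baseline does not count as resolved and T_duration comes out late or missing

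*SAP*

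**What the plan says.** SAP 9.3 lists three linked time parameters for uric acid.

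- T_onset is the "first time point of reduction uric acid concentration >10% of baseline".
- T_resolve is the "first time point of return of uric acid concentration to baseline defined as <10% difference from pre-dose baseline". Section 4.2 has the same definition, and the glossary gives "time of return of uric acid concentration to baseline defined as <10% difference from pre-dose baseline".
- T_duration is described as "Time of duration of effect, calculated as" T_resolve minus T_onset.

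Baseline is fixed in SAP 6.2: "The last non-missing value prior to the start of infusion of any study drug in Period 1 will be used as baseline". On sampling, the protocol synopsis says for the SEL-212 cohorts: "Subjects will return for PK and PD blood draws on Treatment Period 1, Days 1, 7, 14, 21". SAP 9.2 adds the pre-dose Day 28 sample, and schedules a Day 30 sample in Treatment Period 5 only.

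SAP 9.4 summarises the time parameters by "n, minimum, Q1, median, Q3 and maximum". SAP 9.3.1 states: "No further imputation will be applied to any missing values". There is no censoring rule for a subject who never meets the T_resolve definition.

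**The concern.** Effect is lost once uric acid has climbed back to roughly its starting level, and a value above baseline shows this at least as clearly as a value just below it. T_onset has a direction and T_resolve does not. On its plain wording, the T_resolve rule is met only inside a band from 90% to 110% of baseline. Nothing elsewhere in the SAP says that a value above the band counts as resolved.

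The band can be missed because sampling after Day 1 is about weekly. Protocol 4.3.2.3 reports that in Phase I all SEL-212 subjects fell below 0.1 mg/dL within 24 hours, so consecutive samples can run from near zero to above the band. Later chances are few. Under protocol 6.3.1, a SEL-212 subject above 1.0 mg/dL at Day 21 receives no further dose and is followed to about 30 days after the last one. SAP 6.1 lists Early Termination data without summarising them and does not say whether they enter the parameter derivation.

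A complete relapser who stays above the band then has the same blank T_duration as a sustained responder, although the two outcomes are opposite. With 6 to 20 subjects per cohort, one or two lost or lengthened values can move a median or quartile.

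**Working it through.** The plan gives no figure for this parameter, so there is nothing to reproduce. I compared the rule as literally worded with a one-sided rule.

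**Rules**, for baseline B and a post-onset value v:

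- Onset: (B − v)/B > 10%.
- Resolution, literal wording: |v − B|/B < 10%.
- Resolution, one-sided: v ≥ 0.90 × B. This is the exact complement of the onset rule.

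**Illustrative profiles.** B = 8.0 mg/dL, so the literal band is 7.2 to 8.8. Times are hours from the start of SEL-037 on the SAP 9.2 grid for Periods 1–3 (Day 14 = 335 h, Day 21 = 503 h, Day 28 = 671 h). T_onset is 0.5 h in every profile.

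| Profile | T_duration, literal | T_duration, one-sided |
|---|---|---|
| Back to 98% at Day 14 | 335 − 0.5 = 334.5 h | 334.5 h |
| 115% at Day 14, 104% at Day 21 | 503 − 0.5 = 502.5 h (168 h late) | 334.5 h |
| 115% at Day 14, in the band only at Day 28 | 671 − 0.5 = 670.5 h (336 h late) | 334.5 h |
| 115% at Day 14, 115–120% from then on | missing | 334.5 h |
| Sustained responder | missing | missing |

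**How often the upper limit would matter.** The documents give no within-subject CV, so 5% to 12% is an assumption. Suppose the true level has fully returned to baseline, and the baseline and each follow-up value carry independent lognormal error with log-SD equal to the CV. With r = follow-up/baseline, ln r is normal with mean 0 and SD = CV × √2, so

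P(r ≥ 1.10) = 1 − Φ(ln 1.10 / (CV × √2)).

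At CV 10% this is 1 − Φ(0.0953/0.1414) = 1 − Φ(0.674) = 25%. For more than one sample I simulated, because all the samples share the same baseline error. The bottom four rows count relapsers whom the one-sided rule resolves, but whom the literal rule leaves without a value (or, in the last row, resolves late or not at all).

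| Assumed CV | 5% | 8% | 10% | 12% |
|---|---|---|---|---|
| Resolved within two samples, literal | 95% | 83% | 74% | 67% |
| Resolved within two samples, one-sided | 98% | 93% | 90% | 87% |
| No T_resolve solely because of the upper limit, one usable sample | 9% | 20% | 25% | 29% |
| Same, two samples | 3% | 10% | 15% | 20% |
| Same, three samples | 1% | 6% | 9% | 13% |
| Late or missing, two samples | 9% | 21% | 27% | 31% |

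Differences were taken before rounding.

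**Sensitivity to the relapse level.** If residual effect holds the true level at 90% of baseline, the two-sample share without T_resolve falls to 0/2/5/8%. If the true level overshoots to 110%, about half of relapsers or more are late or missing with three samples (50% at CV 5%, 51% at CV 10%).

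**The case against.** The strongest reply is that the SAP never writes a plus-or-minus sign or the word absolute. It speaks of a return to baseline directly after an onset rule framed as a reduction. Read as a pair, the effect begins when the reduction exceeds 10% and ends when it falls below 10%, so 115% of baseline is resolved. That reading is reasonable, and a reader should not take the SAP to state a two-sided rule outright. But the word used is difference, no section supplies the sign, and two programmers could follow the same text and report different durations.

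Two stronger inferences are tempting and should not be drawn. One is that the plan scores such a subject as still under drug effect. The SAP does not say so; the subject simply has no T_resolve, or a late one. The other is that the subjects lost are those with the highest uric acid. In the model above, crossing 110% is measurement noise. Adding an assumed between-subject spread (log-SD 0.2, median 8 mg/dL, CV 10%, two samples), missed and other subjects have nearly the same mean true level (8.17 and 8.16 mg/dL). The missed ones mainly had a low baseline reading (7.40 against 8.34 mg/dL).

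The number of usable samples is also uncertain. Protocol 4.3.2.1 reports diminished activity at Day 14 in 10 subjects (3 + 2 + 3 + 2) given SEL-037 alone in the first Phase I study; relapse that early leaves more samples and a smaller loss. In the other direction, the Day 30 sample is scheduled only for Period 5 and the use of Early Termination data is unclear, which could leave a single sample.

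Finally, little depends on these parameters. They are absent from the key PD parameters and contrasts in SAP 9.7, the box plots in 9.6, the PK/PD correlations and the antibody comparisons. Loss of effect is also visible in Day 21 uric acid, the counts below 6 mg/dL, and the individual listings and profiles. This limits the consequence but does not repair the definition.

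**Conclusion.** The point stands as a defect in a written definition. Taken literally, the T_resolve rule excludes values above 110% of baseline, so T_resolve and T_duration can be late or missing in subjects whose effect has gone. A signed reading would prevent this, and the SAP should say so if it is meant.

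The size is conditional: about 3% to 20% of relapsers with two usable relapse samples would lack T_resolve for this reason alone, 1% to 13% with three, and 9% to 29% with one. These figures rest on an assumed CV of 5% to 12%, independent errors, and full relapse to the true baseline. They are not estimates from trial data.

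The consequence is confined to secondary PD parameters reported as n and quantiles. A reader might infer that the modelled uric acid comparisons are compromised; they are not, because SAP 9.7 does not use T_resolve or T_duration. The change is worth making because these are the SAP's own parameters for duration of effect and the correction costs almost nothing.

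**What to change.** In the glossary, SAP 4.2 and SAP 9.3, define T_resolve as the first time point after T_onset at which uric acid is at or above 90% of the Period 1 baseline, with no upper limit. T_duration then follows without further change.

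The cost is one line of wording in three places and one comparison operator in the program; no new data are needed. The change does not give a value to subjects who never relapse. Treating them as censored at their last sample would be a useful companion sentence, but it is a separate matter.
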